## **19. Potential Benefits to Subjects**

The potential benefits of the proposed research for the research participants are minimal. Any abnormal findings on structural MRI scans will be reported to the participant and/or their doctor per the participant's request. This may lead to early detection of previously unknown abnormalities. However, for the large majority of participants, the proposed research will not have any benefit.

## **20. Recruitment Methods**

The UNM ECT Treatment Program receives referrals from inpatient and outpatient providers at the UNM Mental Health Center. The treatment team will clinically determine who will be eligible for the study and document this in the subject's study records. The research team will only approach patients for the study protocol who speak English and have been identified by the primary treatment team. Patients diagnosed with Major Depression are eligible for ECT treatment will be recruited from the UNM ECT Treatment Program.

## **21. Provisions to Protect the Privacy Interests of Subjects**

The Center for Psychiatry Research handles all confidential data carefully and works to maintain subject privacy and confidentiality. From the standpoint of privacy and confidentiality, the subject's welfare will be safeguarded by responsible, systematically controlled procedures in the collection of information for both clinical and research purposes. In terms of privacy, subjects will first arrive at the research clinic, housed in UNM HSC Center for Psychiatric Research in the Neurobiology Building, [name]. Interaction with subjects will be in the Psychiatry Research Clinic and will only be with relevant staff and/or with family members that they choose to be present. Interviews are held in closed door offices and will be conducted in a manner most comfortable to subjects. Subjects may refuse to answer any question at any time. Recorded information for research purposes will be identified only by subject initials and a study code number. Subject data will be kept in locked cabinets in the research clinic with limited access granted only to designated research personnel. These processes will be in place throughout the entire research process, from initial consenting to research, through research procedures, and follow-up. The study PI will maintain confidentiality of all records to the extent permitted by applicable laws. Records may be inspected by representatives of the study sponsor, the HRRC and other regulatory agencies. If results are presented or published, subjects' identities will remain confidential.

## **22. Economic Burden to Subjects**

The costs of the MRIs and office visits required by the research will be covered by the study. Subjects will be not placed under economic burden due to this trial.

## **23. Compensation**

This study will require attending three visits that will last approximately 2.5 hours for each. Subjects will be compensated \$50.00 for completion of each visit (total subject compensation will be \$150 for the three assessment time-points). Subjects will receive compensation (\$50 merchandise card) at each visit. Social security numbers will not be required for subject payment. The cost of gas/transportation and the inconvenience of participating in this study, make these compensation rates fair and reasonable. Subjects will be reimbursed an additional \$50 merchandise card for participating in the optional EEG to offset additional set-up time.

## **24. Compensation for Research-Related Injury**

UNMHSC will provide subjects with emergency treatment, at their own cost. No commitment is made by the University of New Mexico Health Sciences Center (UNMHSC) to provide free medical care or money for injuries to participants in this study. In the event that you have an injury or illness that is caused by a subject's participation in this study, reimbursement for all related costs of care will be sought from their insurer, managed care plan, or other benefits program. If the subject does not have insurance, they may be responsible for the costs. Subjects will also be responsible for any associated copayments or deductibles required by their insurance.

## **25. Consent Process**

Discussion of the proposed study will occur separate from the evaluation for the ECT procedure. Potential subjects will have ample time to ask questions regarding the nature of this study and will be clearly informed that this imaging investigation is optional. Informed consent will be discussed with each participant with plenty of opportunities to ask questions. The study PI ([name]) or Co-PI ([name]), board-certified psychiatrists with additional fellowship training and certification, will assess decisional capacity for each subject during the consent process. The PI's have extensive experience with the assessment of decisional capacity in both research and clinical domains. All subjects must have decisional capacity to consent to this protocol. Prior to discussion of research participation, the UNM ECT service (Board certified psychiatrists) will assess decisional capacity for the procedure. This assessment will include decisional capacity (ability to communicate choice, appreciate risks/benefits, reason, and manipulate information) and voluntarism capacity.

## **26. Documentation of Consent**

Notes will be kept documenting the informed consent process. Narrative forms will be securely filed with other subject information to document each visit and contact, in addition to required study measures and procedures. Subjects will be given a copy of their signed consent form and HIPAA. A member of the research team will review the HIPAA authorization during the consent.

## **27. Study Test Results/Incidental Findings**

Subjects who receive abnormal MRI scan findings by the neuroradiologist will be notified of an official report by e-mail letting the participant know new results are available and the study PI will communicate the results to the patient. The participant can securely log in to the Mind Research Network COINS homepage to access their MRI radiology report. No sensitive or identifying information is sent via e-mail. If an abnormality that requires follow-up is identified, such as a Doctor Referral recommendation, a hard copy of the report will be mailed to the participant in addition to the e-mail notification. With the patient's permission, the study PI will communicate the results to the patient's primary care providers.

## **28. Progress or Results with Subjects**

The MRI scan is being done to answer research questions, not to examine the subject's brain for medical reasons. This MRI scan is not a substitute for a clinical scan (the type a doctor would order). The research scan may not show problems that may be picked up by a clinical MRI scan. However, all research MRI scans will be read by a neuroradiologist (a doctor with experience reading MRI scans) unless they have been scanned at MRN in the previous six months. If the scan is read, the subject will receive the official report by email. If we find an abnormality that requires urgent follow-up, we will contact the subject by phone to help answer questions and get the right follow-up care. The MRN Medical Director or the research team is always available to answer any questions you may have about the subject's scan.

## **29. Inclusion of Vulnerable Populations**

Sample inclusion will not include gender restrictions. It is expected that our sample will reflect the gender distribution of our ECT service over the last 5 years. Recruitment will reflect the demographics of the state of New Mexico. Prisoners will be excluded from the study. The age range of 50 to 80 years was selected because to limit the variability of age-related volume changes. Subjects with pre-existing diagnoses of neurodegenerative diseases or cerebrovascular pathology will be excluded. However, some older subjects may have significant cognitive deficits prior to treatment related to their depressive episode ("pseudo-dementia"). These subjects may not have decisional capacity for this investigation but are representative of a community sample receiving ECT in this age range. [name] (PI) and [name] (Co-PI) will assess decisional capacity of all subjects participating in this investigation. Subjects that do not have decisional capacity for this investigation will be able to participate in this research if they can assent to the procedure and a legally authorized representative (court appointed mental health treatment guardian) consents to the research protocol.

## **30. Community-Based Participatory Research**

N/A

## **31. Research Involving American Indian/Native Populations**

The proposed research inclusion criteria will be open to all patients with major depressive disorder meeting the inclusion criteria including the clinical indication for ECT. The UNM ECT service is part of a tertiary referral service and the demographics of this service reflect the state of New Mexico. This investigation will not have targeted recruitment outside of routine clinical referrals to the UNM ECT service.

## **32. Transnational Research**

N/A

## **33. Drugs or Devices (see section 9. Resources Available)**

The research involves an investigational device. The Mecta Spectrum 5000Q paired with Soterix Medical 4X1 HD-ECT Multi-Channel Stimulation Interface is intended to reduce ECT current amplitude for amplitude-seizure titration and has received approval from the Food and Drug Administration (refer to “supporting documents”). Digitimer DS8R Biphasic Constant Current Stimulator will be used for motor titration during the second treatment.

These devices will be solely handled and operated by credentialed UNM ECT providers at the UNMH Post Anesthesia Care Unit (inpatient) or UNM Outpatient Surgical Imaging Services (outpatient).

Additionally, the research proposal will use DC-EEG device. The SMARTING (<https://mbraintrain.com/smarting/>) is a small, mobile EEG device that incorporates motion sensors that detect head and body movements. This EEG system will include a 24-channel recording cap. EEG data will be wirelessly recorded to mobile app and is capable of measuring low frequency EEG (< 0.01) pertinent for this proposal.

## **35.CHECKLIST SECTION**

This section contains checklists to provide information on a variety of topics that require special determinations by the IRB. Please complete all checklists relevant to your research.

### **36.Partial Waiver of Consent for Screening/Recruitment**

N/A

### **37.Partial Waiver of HIPAA Authorization for Screening/Recruitment**

N/A

### **38.Waiver of Documentation of Consent**

N/A

### **39.Alteration of Consent**

N/A

### **40.Full Waiver of Consent/Parental Permission**

N/A

### **41.Full Waiver of Consent/Parental Permission (Public Benefit or Service Programs)**

N/A

### **42.Full Waiver of HIPAA Authorization (Checklist)**

N/A

### **43.Other Waiver Types (Checklist)**

N/A

---

### **44.Vulnerable Populations (Checklist)**

#### **A. Adults with Cognitive Impairments**

1. Describe why the objectives of the study cannot be met without inclusion of adults with cognitive impairments.

*Older subjects with major depressive disorder often present with significant cognitive impairment. In the context of ECT response, these patients often have resolution of depression-related cognitive impairment.*

2. Describe how capacity to consent will be evaluated.

*Prior to discussion of research participation, the UNM ECT service (Board-certified psychiatrists) will assess decisional capacity for the procedure. This assessment will include decisional capacity (ability to communicate choice, appreciate risks/benefits, reason, and manipulate information) and voluntarism capacity. If the patient does not have decisional capacity, the subject will not be able to participate in this research.*

3. If subjects may regain capacity to consent, or if subjects may have fluctuating capacity to consent, describe your plans to evaluate capacity to consent throughout the research and to obtain consent to continue participation if capacity is regained.

*In the context of fluctuating consent capacity, the PI and Co-PI will reassess decisional capacity at each study visit. If the subject maintains the minimal threshold to continue with the proposed study, the study team will also include input from surrogate decision maker (power of attorney and/or treatment guardian) to provide additional safeguards. If the subject no longer maintains decisional capacity at a study visit, the subject will be withdrawn from the protocol.*

4. Describe your plans, if any, to provide information about the research to subjects and the steps you will take to assess understanding.

*The study PI ([name]) and Co-PI ([name]) are board-certified psychiatrists with fellowship training in geriatric psychiatric and psychosomatic medicine and will be involved with the consent process for all study participants. They will assess decisional capacity at all three study time points.*

5. Describe your plans to obtain assent, including whether assent will be obtained from none, some, or all subjects.

*All subjects must have decisional capacity to consent to this protocol.*

6. Describe why risks to subjects are reasonable in relation to anticipated benefits to the subjects.

*The risks of low-amplitude seizure and motor titration will be minimal relative to the traditional (higher) ECT amplitudes. The experimental portion of this protocol is relevant only to the first treatment with the remaining treatments completed at the traditional 800 mA amplitudes. Subjects will also receive more comprehensive clinical and neuropsychological assessments by participating in this research protocol relative to routine clinical care.*

7. If this study involves a health or behavioral intervention, describe why the relation of the anticipated benefit to the risk of the research is at least as favorable to the subjects as that presented by alternative procedures.

*This investigation proposes use amplitude titration relative to the traditional pulse-number based titration and fixed amplitude ECT. This difference is only relevant to the first treatment. The remaining treatments will be completed with traditional 800 mA ECT.*

8. Describe your plans for monitoring the well-being of subjects including any plans to withdraw subjects from the research if they appear to be unduly distressed.

*Subjects that appear to be distressed will be encouraged to withdraw from the study protocol. If subjects appear to be unduly distressed, the study PI will withdraw these subjects from the protocol. Data regarding subject drop-out will be documented and presented to the DSMB.*

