Amplitude titration, as proposed here, can reduce the variability related to fixed amplitude dosing and optimize clinical and cognitive outcomes. *The goal of this project is to change standard ECT parameter selection from a fixed amplitude with variable pulse number (combination of pulse train duration and frequency) to an individualized and empirically determined amplitude with fixed pulse number.* To achieve this goal, we will focus on the relationship between amplitude titrated seizure threshold and treatment-responsive changes in hippocampal neuroplasticity with RUL fixed amplitude ECT. Fixed amplitude ECT results in variable E-fields and inconsistent changes in hippocampal neuroplasticity. In contrast, computational and pre-translational investigations have demonstrated that amplitude titration results in consistent E-fields. Seizure titration amplitudes (based on historic data, 233 to 544 mA) are below the amplitude range of FDA-approved ECT devices (500 to 900 mA) and will require an adaptor to reduce the amplitude (FDA Investigational Device Exemption). Amplitude titration will also be below the hippocampal neuroplasticity threshold and insufficient for antidepressant response. The difference between RUL amplitude titration and RUL fixed amplitude (800 mA) ECT will determine the degree of target engagement with the hippocampus. To illustrate, subjects with low amplitude seizure threshold of ~250 mA (800/250, high fixed/titration amplitude ratio) will have significant changes in hippocampal neuroplasticity. Subjects with high amplitude ~500 mA (800/500, low fixed/titration ratio) will have minimal changes in hippocampal neuroplasticity. The relationship between amplitude titration and fixed amplitude hippocampal neuroplasticity will be used to develop the amplitude multiplier required for consistent and clinically effective ECT dosing. Amplitude titration with

multiplier will be associated with the “sweet spot” for hippocampal neuroplasticity: sufficient for antidepressant response but not excessive thus resulting in cognitive safety.

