the degree of target engagement with the hippocampus. To illustrate, subjects with low amplitude titration of ~250 mA (800/250, high fixed/titration amplitude ratio) will have significant changes in hippocampal neuroplasticity. Subjects with high amplitude titration ~500 mA (800/500, low fixed/titration ratio) will have minimal changes in hippocampal neuroplasticity. The relationship between amplitude titration and fixed amplitude hippocampal neuroplasticity will be used to develop the amplitude multiplier required for consistent and clinically effective ECT dosing. A randomized controlled trial will then compare hippocampal neuroplasticity, antidepressant, and cognitive outcomes between amplitude titration with neuroplasticity multiplier (fixed pulse number) and traditional fixed amplitude ECT (800 mA, variable pulse number) in older depressed subjects.

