### 3. Study Design

Subjects will receive their baseline imaging, clinical, and neuropsychological assessment 24 to 48 hours prior to the first ECT session (V1). Subjects will first receive RUL amplitude titration (first treatment) and then RUL fixed amplitude (800 mA) and fixed pulse number ECT (subsequent treatments). We will 1) verify results from pre-translational investigations that demonstrated the relationship between current pulse amplitude and a whole brain E-field metric ( $I/E_{brain}$ ), and 2) determine the relationship between current pulse amplitude and treatment-responsive changes in hippocampal neuroplasticity from RUL fixed-amplitude (800 mA) ECT. Treatments will continue thrice weekly until clinical response, which typically occurs between six and twelve treatments . Subjects will receive their second assessment (V2) one day after the sixth ECT treatment and the final assessment (V3) one day after the ECT series. Subjects who do not demonstrate improvement by the V2 assessment (< 25% reduction from baseline IDS-C30 total score) will transition to traditional BT for the remainder of the ECT series. The anesthesiologist will determine the appropriate dose of methohexitol (general anesthetic) and succinylcholine (depolarizing neuromuscular blocker). Anesthetic medications, electroencephalographic seizure duration, motor seizure duration, and maximum ictal heart rate will be recorded for each treatment.

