Subjects (n = 40) will receive amplitude titrated seizure threshold during the first treatment with RUL . The Soterix 4X1 High Definition ECT Multi-channel Stimulation Interface (“Soterix Interface”) is a passive amplitude reducer for the MECTA 5000Q. The Soterix Interface reduces the amplitude range to 200 mA and permits 50 mA incremental dosing throughout the 200 to 900 mA dosing range. Pulse width (1.0 ms), pulse train duration (8 s), and frequency (20 Hz, 320 pulses) will be fixed for amplitude titration. Subjects will receive stimulations starting with 200 mA with 50 mA increases until seizure activity is initiated. Clinical judgement will define seizure adequacy based on duration and morphology. In addition, subjects will receive amplitude titrated motor threshold after administration of general anesthesia during the second ECT treatment (exploratory aim, see “Motor Titration” below). After amplitude titrated seizure threshold, subsequent treatments will be completed with RUL fixed 800 mA with the same pulse width (1.0 ms) and pulse number (8 s, 20 Hz, and 320 pulses). If the subject fails to demonstrate improvement at V2 (< 25% reduction from baseline IDS-C30 total score), the subject will then receive traditional BT for the remainder of the ECT series.

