## **14. Provisions to Monitor the Data to Ensure the Safety of Subjects**

Data safety and monitoring will be carried out to ensure and maintain the scientific integrity of this project and to protect the safety of our participants. Safety monitoring is the process during the study that involves review of accumulated outcome data for groups of subjects to determine if any of the procedures practiced should be altered or stopped. Ultimately, the PI ([name]) will be responsible for monitoring the safety of the study and complying with the reporting requirements. An independent Data Safety and Monitoring Board (DSMB) will review the study data on a biennial basis with the PI to ensure participant safety (re: subject recruitment at 20 subjects/year, DSMB meetings every ~ 10 participants). The Data Safety and Monitoring Board will include [name] [name] (DSMB Chair/Dept. of Neurology), [name] (Dept. of Anesthesiology), and [name] (PI at Mind Research Network). The board members have no conflicts of interest or roles with the current project. Drs. [name] and [name] have experience participating in ECT-related DSMB, and [name] has extensive clinical experience with ECT. Continuous, close monitoring of participant safety will include prompt and frequent reporting of safety data (i.e., adverse/serious adverse events) to the DMSB, the University of New Mexico Health Sciences Center Institutional Review Board (UNMHSC IRB) and/or appropriate NIH staff with oversight responsibility. The focus of adverse event reporting will be the first treatment of the ECT series, which is the only experimental treatment for this phase of the project. The first treatment will be amplitude titration (as opposed to the more traditional titration based on pulse number or frequency). The amplitude titration will result in reduced amplitudes (hypothesized range will be between 250 and 550mA, traditional ECT is conducted at 800mA). Adverse events may include expected side effects related to ECT: headaches, nausea (from anesthesia), and muscle aches (from anesthesia). Unexpected side effects (to be determined) will also be reviewed with the DSMB. In addition, relevant published data related to the study protocol will also be presented to the DSMB. The DSMB will evaluate the adverse effects of the first treatment in relation to the expected side effects related to a traditional ECT series. The PI will provide a summary of the safe conduct of the study to NIH and FDA on an annual basis as part of the progress report. All AEs occurring during the course of the study will be collected, documented, and reported to the UNMHSC IRB. The review of data may result in early termination of the study, amendment to the protocol, or changes to

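### By the protocol's own definition, right unilateral treatments 2 onward match traditional ECT in amplitude but not in pulse number, so the statements that only treatment 1 departs from it are wrong as written

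*Protocol*

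**What the plan says.** The Protocol makes three sets of statements that bear on this point.

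**What traditional ECT is.** Section 1 gives the project's aim as to "change standard ECT parameter selection from a fixed amplitude with variable pulse number (combination of pulse train duration and frequency") towards an individualised amplitude with a fixed pulse number. Section 2 describes the comparator of the planned randomised trial as "traditional fixed amplitude ECT (800 mA, variable pulse number) in older depressed subjects".

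**What subjects receive from treatment 2 on.** Section 3 specifies "RUL fixed amplitude (800 mA) and fixed pulse number ECT (subsequent treatments"). It then adds that "subsequent treatments will be completed with RUL fixed 800 mA with the same pulse width (1.0 ms) and pulse number" as in the titration session, namely 8 s, 20 Hz and 320 pulses. Section 12 repeats these settings and calls only the amplitude traditional. Sections 3, 12 and 33 also place a motor titration at the second treatment.

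**How those treatments are labelled.** In Section 44, A.7 says: "This difference is only relevant to the first treatment. The remaining treatments will be completed with traditional 800 mA ECT." A.6 says: "The experimental portion of this protocol is relevant only to the first treatment with the remaining treatments completed at the traditional 800 mA amplitudes." Section 14 directs adverse-event reporting to the first treatment, "which is the only experimental treatment for this phase of the project".

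**The concern.** The three sets of statements cannot all be true. If traditional ECT varies the pulse number, a course that holds it at 320 for every subject is not traditional in that respect, and the difference does not end with the first treatment.

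The label carries weight in two places. A.7 asks why the balance of benefit and risk is at least as favourable as that of alternative procedures. For treatments 2 onward, the answer rests on their being traditional. Section 14 uses the same premise to set the scope of oversight: the adverse-event focus, the DSMB's evaluation of adverse effects, and the events that would lead to suspension or termination are all tied to treatment 1. Followed as written, those rules leave a setting that the research itself prescribes outside their stated scope.

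**Working it through.** **1. The plan's own figure.** The inputs are in Protocol Sections 3 and 12: frequency 20 Hz, train duration 8 s, pulse width 1.0 ms, amplitude 800 mA.

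Pulse number = pulses per cycle × frequency × duration = 2 × 20 × 8 = 320, as stated. Two pulses per cycle is an assumption; one per cycle gives 1 × 20 × 8 = 160 and does not match.

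**2. What is constant from treatment 2 on.** Charge = amplitude × pulse width × pulse number = 0.8 A × 1.0 ms × 320 = 256 mC. It is the same for every subject at every right unilateral treatment, until any switch to bitemporal placement after V2. The documents give no pulse number for traditional ECT, so this figure has no comparator and does not measure the departure.

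**3. Definition against regimen.**

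| Feature | Traditional or standard ECT (Sections 1, 2) | Treatments 2 onward (Sections 1, 3, 12, 33) | Agree? |
|---|---|---|---|
| Amplitude | Fixed; 800 mA for the planned comparator | Fixed at 800 mA | Yes |
| Pulse number | Variable | 320 for every subject | No |
| Motor titration | Not mentioned | Done at treatment 2, as an exploratory aim | No |

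The pulse-number row contradicts the last sentence of A.7. The last two rows contradict the limiting of the experimental part to treatment 1 in A.6 and Section 14. A.6 itself mentions the risk of motor titration just before it confines the experimental portion to the first treatment.

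**4. Extent.** V2 follows the sixth treatment and treatment 1 is the titration session, so 6 − 1 = 5 of the 6 treatments before V2 are affected. For a subject who stays on right unilateral placement through a series of six to twelve treatments (the typical range in Section 3), the count is 5 to 11.

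**5. What is not touched.** The H1 and H2 sample sizes can be reproduced without any pulse number. For H1, the Fisher z formula with r = 0.5, one-sided 0.025 and 80% power gives 29.01, against 29 stated. For H2, the overall F test with 3 numerator degrees of freedom, f² = 0.35, level 0.05 and 80% power gives 36, as stated. The design sections describe the fixed-pulse regimen correctly, so the hypotheses are tested on the treatment actually given.

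**The case against.** A fair defence has four parts.

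- **A.7 can be read narrowly.** Its first sentence contrasts amplitude titration with pulse-number titration, and seizure titration does happen only at treatment 1. A.6 and Section 12 use the word traditional for the amplitude alone, which is accurate. This stands, but it does not rescue A.7's closing sentence, which applies the label to the treatments as a whole, or the wording in A.6 and Section 14 that confines the experimental part to treatment 1.
- **The fixed pulse number is openly stated and has a purpose.** Holding pulse settings constant makes 800 divided by threshold a pure amplitude ratio, as H2 needs, and matches the amplitude-titration arm of the planned trial. This stands. The design choice is not criticised here, but its purpose confirms that the research prescribes the setting.
- **Oversight is wider than treatment 1.** Under Section 14 the DSMB reviews the study data and all adverse events go to the IRB. A.8 sends drop-out data to the DSMB, and V2 checks each subject's response. This stands: a focus is not an exclusion, and a reader should not infer that later treatments go unseen. What remains is that the adverse-effect evaluation and the suspension rule name treatment 1 only.
- **Nothing shows harm.** This also stands.

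Three stronger inferences are tempting and not supported.

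- A reader might conclude that the depression results will be benchmarked as traditional ECT. No passage makes that comparison; this phase has a single arm, and the planned trial has its own traditional arm.
- A reader might take the spread in multiples of threshold, 800/233 = 3.43 down to 800/544 = 1.47 over the historic range, as the size of the problem. That spread follows from fixed amplitude, which traditional ECT shares and to which the Protocol itself attributes variable effects.
- A reader might infer that pulse number is the only parameter individualised in traditional ECT. The documents do not say so.

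**Conclusion.** The contradiction is in the text. By the Protocol's own definition, right unilateral treatments 2 onward are traditional in amplitude and not in pulse number, and motor titration adds a research procedure at treatment 2. The statements in A.6, A.7 and Section 14 that confine the departure or the experimental part to treatment 1 are wrong as written.

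This is more than clerical, because the benefit-risk answer and the stated scope of the safety rules rest on them. It is also bounded. It reaches every subject and 5 of the 6 treatments before V2, but its clinical size cannot be computed, and the documents give no ground for saying that risk is higher or lower. H1, H2 and the sample size stand.

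The conclusion assumes that the descriptions in Sections 1 and 2 are what the Protocol means by traditional or standard ECT; no other definition is given.

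**What to change.** Reconcile Protocol Sections 1, 2, 3 and 12 with Section 14 and with Section 44, A.6 and A.7. No dose or clinical rule is proposed here, and which text should change is for the sponsor to decide.

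If pulse number stays fixed from treatment 2 on:

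- State in A.6, A.7 and Section 14 that the fixed pulse number is part of the research regimen, and acknowledge the motor titration at treatment 2.
- Rest the A.7 answer on the regimen actually given.
- Extend the adverse-event focus, the DSMB evaluation and the suspension wording in Section 14 to all research-specified right unilateral treatments.
- Describe any outcomes carried into the planned trial as those of 800 mA with 320 fixed pulses.

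The cost is protocol wording and an IRB amendment. The statement that only the first treatment is experimental would also become less favourable. No new data collection or change to the analysis is needed.
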